1. SITE INFORMATION

| | | |
|-------------|-------------------------|-----------------------|
| Site Number | Investigator | Country |
| _ _ _ _ | | |
| Reporter | Phone Number () () | Fax Number () () |

2. SUBJECT INFORMATION

| | | | | |
|-----------------------------|--------------------|--|------|--|
| Subject ID Number | Age at event onset | Sex  F  M | Race | If applicable, provide End of Study date |
| _ _ _ _ _ _ _ _ _ _ _ _ _ _ | | | | |

If this is a follow-up to an event reported in the EDC system (eg, Rave), provide the adverse event term: _____
 and start date: Day ____ Month ____ Year ____

3. SERIOUS ADVERSE EVENT

Provide the date the Investigator became aware of this information: Day ____ Month ____ Year ____

| Serious Adverse Event diagnosis or syndrome If diagnosis is unknown, enter signs / symptoms and provide diagnosis, when known, in a follow-up report. <small>List one event per line. If event is fatal, enter the cause of death. Entry of "death" is not acceptable, as this is an outcome.</small> | Date Started | | Date Ended | | Check only if event occurred before first dose of IP | Is event serious?  No  Yes | Serious enter Serious Criteria code (see codes below) | Relationship Is there a reasonable possibility that the Event may have been caused by IP or an Amgen device used to administer the IP? | | | | Outcome of Event Resolved Not resolved Fatal Unknown | Check only if event is related to study procedure eg, biopsy | | |
|--|--------------|-------|------------|-----|--|---|---|---|------|---------|--|--|---|----|--|
| | Day | Month | Year | Day | | | | Month | Year | -Fatal- | | | | | |
| | No | | Yes | | | | | No | | Yes | | | | No | |
| | | | | | | | | | | | | | | | |
| | | | | | | | | | | | | | | | |
| | | | | | | | | | | | | | | | |
| | | | | | | | | | | | | | | | |

Serious Criteria: 01 Fatal 02 Immediately life-threatening 03 Required/prolonged hospitalization 04 Persistent or significant disability /incapacity 05 Congenital anomaly / birth defect 06 Other medically important serious event

4. Was subject hospitalized or was a hospitalization prolonged due this event? No Yes If yes, please complete all of Section 4

| | |
|--|--|
| Date Admitted Day ____ Month ____ Year ____ | Date Discharged Day ____ Month ____ Year ____ |
|--|--|

5. Was IP/drug under study administered/taken prior to this event? No Yes If yes, please complete all of Section 5

| IP/Amgen Device: | Date of Initial Dose Day ____ Month ____ Year ____ | Prior to, or at time of Event | | | | Frequency | Action Taken with Product 01 Still being Administered 02 Permanently discontinued 03 Withheld | Lot # and Serial # |
|--|---|---|------|-------|--|-----------|--|---|
| | | Date of Dose Day ____ Month ____ Year ____ | Dose | Route | | | | |
| | | | | | | | | |
| <<IP/Device>>  blinded  open label | | | | | | | | Lot # _____  Unknown Serial # _____  Unavailable / Unknown |
| <<IP/Device>>  blinded  open label | | | | | | | | Lot # _____  Unknown Serial # _____  Unavailable / Unknown |

FORM-056000

Version 7.0 Effective Date: 1 February 2010

Approved

| | |
|---|--|
| AMGEN Study # 20160132 AMG 596 | Electronic Serious Adverse Event Contingency Report Form For Restricted Use |
|---|--|

| | Site Number | Subject ID Number | | | | | | | | | | | | | |
|--|------------------|-------------------|------|-----------|-------|---------|------------|-----|------------|-----|-------|-------|-------|---------------|-----|
| 6. CONCOMITANT MEDICATIONS (eg, chemotherapy) Any Medications?  No  Yes if yes, please complete: | | | | | | | | | | | | | | | |
| Medication Name(s) | Start Date | | | Stop Date | | | Co-suspect | | Continuing | | Dose | Route | Freq. | Treatment Med | |
| | Day | Month | Year | Day | Month | Year | No | Yes | No | Yes | | | | No | Yes |
| | | | | | | | | | | | | | | | |
| | | | | | | | | | | | | | | | |
| | | | | | | | | | | | | | | | |
| | | | | | | | | | | | | | | | |
| 7. RELEVANT MEDICAL HISTORY (include dates, allergies and any relevant prior therapy) | | | | | | | | | | | | | | | |
| | | | | | | | | | | | | | | | |
| | | | | | | | | | | | | | | | |
| | | | | | | | | | | | | | | | |
| 8. RELEVANT LABORATORY VALUES (include baseline values) Any Relevant Laboratory values?  No  Yes if yes, please complete: | | | | | | | | | | | | | | | |
| Date | Test | Unit | | | | | | | | | | | | | |
| | | | | | | | | | | | | | | | |
| Day | Month | Year | | | | | | | | | | | | | |
| | | | | | | | | | | | | | | | |
| | | | | | | | | | | | | | | | |
| | | | | | | | | | | | | | | | |
| 9. OTHER RELEVANT TESTS (diagnostics and procedures) Any Other Relevant tests?  No  Yes if yes, please complete: | | | | | | | | | | | | | | | |
| Date | Additional Tests | | | | | Results | | | | | Units | | | | |
| Day | Month | Year | | | | | | | | | | | | | |
| | | | | | | | | | | | | | | | |
| | | | | | | | | | | | | | | | |

Approved

Appendix C. Pregnancy and Lactation Notification Worksheets

AMGEN Pregnancy Notification Worksheet
 Fax Completed Form to the Country-respective Safety Fax Line
SELECT OR TYPE IN A FAX#

1. Case Administrative Information
 Protocol/Study Number: 20160132
 Study Design: Interventional Observational (If Observational: Prospective Retrospective)

2. Contact Information
 Investigator Name _____ Site # _____
 Phone (____) _____ Fax (____) _____ Email _____
 Institution _____
 Address _____

3. Subject Information
 Subject ID # _____ Subject Gender: Female Male Subject DOB: mm ____ / dd ____ / yyyy ____

4. Amgen Product Exposure

| Amgen Product | Dose at time of conception | Frequency | Route | Start Date |
|---------------|----------------------------|-----------|-------|-------------------------------|
| | | | | mm ____ / dd ____ / yyyy ____ |

Was the Amgen product (or study drug) discontinued? Yes No
 If yes, provide product (or study drug) stop date: mm ____ / dd ____ / yyyy ____
 Did the subject withdraw from the study? Yes No

5. Pregnancy Information
 Pregnant female's LMP mm ____ / dd ____ / yyyy ____ Unknown
 Estimated date of delivery mm ____ / dd ____ / yyyy ____ Unknown N/A
 If N/A, date of termination (actual or planned) mm ____ / dd ____ / yyyy ____
 Has the pregnant female already delivered? Yes No Unknown N/A
 If yes, provide date of delivery: mm ____ / dd ____ / yyyy ____
 Was the infant healthy? Yes No Unknown N/A
 If any Adverse Event was experienced by the infant, provide brief details: _____

Form Completed by:
 Print Name: _____ Title: _____
 Signature: _____ Date: _____

Approved

AMGEN Lactation Notification Worksheet

Fax Completed Form to the Country-respective Safety Fax Line

SELECT OR TYPE IN A FAX#

1. Case Administrative Information
Protocol/Study Number:
Study Design: Interventional Observational (If Observational: Prospective Retrospective)

2. Contact Information
Investigator Name Site #
Phone () Fax () Email
Institution
Address

3. Subject Information
Subject ID # Subject Date of Birth: mm / dd / yyyy

4. Amgen Product Exposure

| Amgen Product | Dose at time of breast feeding | Frequency | Route | Start Date |
|----------------------|--------------------------------|----------------------|----------------------|---|
|  |  |  |  | mm  / dd  / yyyy  |

Was the Amgen product (or study drug) discontinued? Yes No
If yes, provide product (or study drug) stop date: mm / dd / yyyy
Did the subject withdraw from the study? Yes No

5. Breast Feeding Information
Did the mother breastfeed or provide the infant with pumped breast milk while actively taking an Amgen product? Yes No
If No, provide stop date: mm / dd / yyyy
Infant date of birth: mm / dd / yyyy
Infant gender: Female Male
Is the infant healthy? Yes No Unknown N/A
If any Adverse Event was experienced by the mother or the infant, provide brief details:

Form Completed by:
Print Name: Title:
Signature: Date:

Approved

Appendix D. Modified Response Assessment In Neuro-Oncology (RANO)

The RANO criteria are extensions to the Macdonald criteria that incorporate T2/ FLAIR images to better capture lesion response (Wen et al, 2010). Here, the RANO criteria are further modified to capture pseudoprogression and delayed responses which may be observed in response to immunotherapies (Okada et al, 2015).

Patients require at least 1 bi-dimensionally measurable contrast-enhancing lesion that can be accurately assessed at baseline by magnetic resonance imaging (MRI) to be included in this a study.

Definitions:

- Measurable lesions contrast-enhancing lesions that can accurately be measured bidimensionally with $\geq 10\text{mm}$ longest diameter and $\geq 10\text{mm}$ perpendicular diameter and noted on more than one imaging slice.
- Non-measurable lesions – all other lesions, including small lesions, ie, bone lesions, leptomeningeal disease and cystic lesions that are not confirmed and followed by imaging techniques.

Documentation of index and non-index lesions:

- Index Lesions
 - All measureable lesions (up to 5) should be identified as index lesions, measured and recorded during screening.
 - Enhancing lesions should be selected based on size (largest cross-sectional area) and suitability for accurate repeat measure (clearly defined borders)
 - The sum of bidimensional products (total cross-sectional area of measurable lesions) for all enhancing measurable lesions at screening will be calculated and reported as the baseline disease burden.
 - Baseline disease burden will be the reference used to characterize radiographic objective tumor response.
 - Baseline or nadir, whichever is smaller, is used to calculate PD.
- Non-Index Lesions
 - All other lesions (or sites of disease) should be identified and recorded as non-index lesions during screening.
 - Measurable lesions located in previously irradiated sites that have not since shown documented progression are non-index lesions.
 - Incidental new lesions will be recorded and tracked as non-index lesions.
 - Measurement of non-index lesions is not required, but absence or presence and qualitative changes (unequivocal response, stable, unequivocal progression) should be recorded throughout the study.

Approved

Table 21. Measurement Summary

| Imaging modality | MRI |
|-----------------------------|--|
| Sequences for this protocol | 
 - Axial Pre Contrast (2D) T1 - Axial T2/FLAIR - Axial T2 - Axial Post Contrast (2D) T1 - Axial DWI (at selected sites) - Sagittal Post Contrast (3D) T1 (at selected sites) |
| Measurement technique | Bidimensional; sum of products of perpendicular diameters |
| Imaging intervals | Screening, every 10-12 weeks, SFUP, LTFU |
| Measurable lesions | Contrast-enhancing lesions with ≥ 10 mm longest diameter and ≥ 10 mm perpendicular diameter |
| Measurable disease | One to five index lesions |

Table 22. Response Assessment

| All % changes are calculated as change from baseline burden, except PD which is baseline or nadir. | |
|--|--|
| Complete response (CR) | 
 • Disappearance of all enhancing disease • no new lesions • stable or improved T2/FLAIR • no more than physiological steroids • clinically stable or improved • Disappearance confirmed with follow-up scan after ≥ 4 weeks |
| Partial response (PR) | 
 • $\geq 50\%$ decrease in the sum of perpendicular diameters of enhancing disease from baseline • stable or improved T2/FLAIR • stable or decreased steroid dose • clinically stable or improved • Decrease confirmed with follow-up scan after ≥ 4 weeks |
| Stable disease (SD) | 
 • Changes do not qualify for CR, PR or PD • stable or improved T2/FLAIR • stable or decreased steroid dose • clinically stable or improved |
| Progressive disease (PD) | 
Any of the below
 
 • $\geq 25\%$ increase in the sum of perpendicular diameters of enhancing disease from the lesser of baseline or nadir • or substantially worsened T2/FLAIR • or unequivocal progression in new lesions • or substantial clinical decline • Increase confirmed with follow-up scan ≥ 4 weeks after initial observation. |

Reponses (CR and PR) are dated at time of confirmation scan.

Progression (PD) is backdated to initial observation, if confirmed.

Approved

Patients with a neurological decline attributable to their underlying tumor requiring discontinuation of treatment without objective evidence of measurable radiographic disease progression at that time should be classified as having “clinical deterioration.” Every effort should be made to document the radiographic progression even after discontinuation of treatment.

Approved

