4. SUBJECT ELIGIBILITY

4.1 Inclusion Criteria

101. Subject has provided written informed consent prior to initiation of any study-specific activities/procedures
102. Male or female, of at least 18 years of age

103. Eastern Cooperative Oncology Group (ECOG, [Appendix F](#)) Performance Status of ≤ 1
104. Life expectancy of at least 3 months, in the opinion of the investigator.
105. Must have pathologically documented, and definitively diagnosed World Health Organization (WHO) grade 4, glioblastoma or lower grade malignant gliomas with EGFRvIII positive tumor
106. Must have recurrent disease confirmed by MRI (Group 1) or completed SoC therapy such as surgery with adjuvant radiochemotherapy with or without maintenance temozolomide according to local standards for newly diagnosed disease (Group 2)
107. Group 1 subjects must have ≥ 1 index lesion by modified RANO criteria ([Appendix D](#)), exemption: non-measurable disease is allowed for subjects with re-surgery (surgery for recurrent disease) before start of screening; Group 2 subjects must have radiographically measurable disease or non-measurable disease by modified RANO criteria or both at the time of enrollment are allowed:
 - Bidimensionally measurable, contrast-enhancing lesions with clearly defined margins by MRI with perpendicular diameters of at least 10 mm x 10 mm and noted in more than one imaging slice
 - Imaging must be performed within 14 days of enrollment. Subject can be on stable dose steroid medication (systemic corticosteroid doses of ≤ 2 mg of dexamethasone (or equivalent) per day after consultation with Sponsor) for at least 5 days immediately before and during imaging study
108. Confirmed EGFRvIII positivity from pre-screening or confirmation at time of study enrollment required if prior treatment included EGFRvIII – or amplified EGFR- targeted therapy (one test sufficient, please refer to [Section 7.2.1](#))
109. Archived tumor tissue from initial diagnosis or subsequent relapse for submission to central review
110. Hematological function as follows:
 - Absolute neutrophil count (ANC) $> 1500/\text{mm}^3$ ($1.5 \times 10^9/\text{L}$)
 - Platelet count $> 100,000/\text{mm}^3$ ($100 \times 10^9/\text{L}$)
 - White blood cell (WBC) count $> 3 \times 10^9/\text{L}$
 - Hemoglobin > 9.0 g/dL

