If a subject has no tumor evaluation in the study, progression-free survival time will be censored at the date of the first administration of AMG 596.

Subjects who withdraw consent to participate in the study prior to disease progression will be censored at their last evaluable radiological assessment date.

Response Criteria (per modified RANO):

Complete Response (CR):

- Disappearance of all enhancing disease
- No new lesions
- Stable or improved T2/FLAIR
- No more than physiological steroids
- Clinically stable or improved
- Disappearance confirmed with follow-up scan after ≥ 4 weeks

Partial Response (PR):

- $\geq 50\%$ decrease in the sum of perpendicular diameters of enhancing disease from baseline
- Stable or improved T2/FLAIR
- Stable or decreased steroid dose
- Clinically stable or improved
- Decrease confirmed with follow-up scan after ≥ 4 weeks

Stable Disease (SD):

- Changes do not qualify for CR, PR or PD
- Stable or improved T2/FLAIR
- Stable or decreased steroid dose
- Clinically stable or improved

Progressive Disease (PD):

Any of the below

- $\geq 25\%$ increase in the sum of perpendicular diameters of enhancing disease from the lesser of baseline or nadir
- Or substantially worsened T2/FLAIR
- Or unequivocal progression in new lesions
- Or substantial clinical decline
- Increase confirmed with follow-up scan ≥ 4 weeks after initial observation.

Screening Date:

Screening date is defined as the date the informed consent was signed.

Study Day 1:

Day 1 is defined as the first day that investigational product is administered to the subject. The day before Day 1 is referenced as Day-1.

Study Day:

Post day of dose: study day = (study date - date of Study Day 1) + 1

Pre day of dose: study day = (study date – date of Study Day 1)

Time to Response:

Time to response is calculated as the number of days from the date of first administration of AMG 596 to the date of confirmation of first objective response per MRI scan (date of confirmation of first objective response – date of first dose of AMG 596+1).

If a subject did not respond, time to response will be censored at the date of the last evaluable response assessment.

If a subject has no tumor evaluation related to response assessment as per modified RANO criteria, time to response will be censored at the date of the first administration of AMG 596.

Time to Progression:

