9.5 Efficacy Analyses

Unless otherwise specified, all subjects that are enrolled and receive at least one administration of AMG 596 at the MTD (the efficacy analysis set) will be included in the analysis of the secondary efficacy endpoints.

The following methods will be used with Kaplan-Meier analyses of efficacy endpoints.

- Estimation of the median and CI will use the Brookmeyer and Crowley (1982) method
- Landmark estimates (eg, 6 month PFS) will be estimated using the Kaplan-Meier curve and CI using Greenwood's formula to estimate the standard error (see [Kalbfleisch J.D. and Prentice R.L. \(1980\)](#))

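### Recorded progression of baseline non-index lesions enters no PD line, so enhancing growth with stable T2/FLAIR can go uncounted and can bias the SAP's PFS and TTP upward

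*Protocol*

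**What the plan says.** Protocol Appendix D separates index lesions, which are measured, from non-index lesions, which need not be. For non-index lesions, "absence or presence and qualitative changes (unequivocal response, stable, unequivocal progression) should be recorded throughout the study". The class covers every other lesion or site of disease, and it includes some large ones: "Measurable lesions located in previously irradiated sites that have not since shown documented progression are non-index lesions".

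Table 22 gives four routes to PD: a rise of at least 25% in the bidimensional sum from baseline or nadir, substantially worse T2/FLAIR, "or unequivocal progression in new lesions", and substantial clinical decline. SAP section 5 has the same third route ("Or unequivocal progression in new lesions"), and SAP Appendix D repeats the table. The CR row excludes new lesions. The PR row has no condition on new or non-index lesions.

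Criterion 107 (protocol section 4.1) requires an index lesion in Group 1 with one exemption: "non-measurable disease is allowed for subjects with re-surgery (surgery for recurrent disease) before start of screening". It admits Group 2 subjects with measurable disease, non-measurable disease or both. Appendix D, by contrast, states that at least one measurable lesion is required for inclusion.

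By default, the SAP's secondary efficacy endpoints are analysed on "all subjects that are enrolled and receive at least one administration of AMG 596 at the MTD" (section 9.5), with the RANO Evaluable set named only for ORR and response category. Protocol section 10.5.3 uses the RANO Evaluable set for ORR and, among the same subjects, for the 6- and 12-month progression-free proportions.

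**The concern.** Sites are asked to record a progression grade that the response table then ignores for disease present at entry. A subject without an index lesion has no baseline sum, so the 25% rule has nothing to work on. Existing enhancing disease can then grow without meeting a radiographic PD line, provided T2/FLAIR stays stable and no new lesion progresses. Under the SAP such a subject stays at risk, or is censored at a later scan, when an event should have been counted. That can lengthen PFS and TTP. In subjects who do have index lesions, PR can be declared on the measured sum while a baseline non-index lesion unequivocally progresses.

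**Working it through.** The plan states no figure for this point, so the main check sets the rules side by side.

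**Step 1. What each PD line does with a growing enhancing non-index lesion present at baseline**

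| PD line (Table 22) | Does it catch the growth? |
|---|---|
| Rise of at least 25% in the sum | Not reliably. The baseline burden is built from enhancing lesions measurable at screening, and non-index lesions need not be measured. With no index lesion the baseline is empty and a percentage change is undefined. |
| T2/FLAIR substantially worse | Only if T2/FLAIR changes as well. It does not use the recorded lesion grade. |
| Progression in new lesions | No. The lesion is not new. |
| Clinical decline | Only if the subject declines. SAP section 5 counts radiological progression or death for PFS and radiographic PD for TTP, so clinical decline alone is not an event in either. |

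Example: a Group 1 subject enters after re-surgery with an 8 mm enhancing remnant, below the 10 mm x 10 mm threshold. It grows with stable T2/FLAIR and no new lesion. No radiographic line is clearly met, although the site records unequivocal progression.

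**Step 2. The response rows.** A persisting enhancing non-index lesion blocks CR, which needs all enhancing disease gone. Its growth blocks neither PR nor SD. Growth that worsens T2/FLAIR does block PR, which requires stable or improved T2/FLAIR. A new lesion that itself unequivocally progresses is PD. One that merely appears is not PD and does not block PR. No precedence is stated for a subject meeting both a PR row and a PD line.

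**Step 3. Where it enters the analysis**
- SAP Kaplan-Meier PFS and TTP: all subjects dosed at the MTD, including those with no index lesion. Fully exposed.
- Protocol 6- and 12-month proportions: RANO Evaluable set. Exposed only through subjects with measurable disease who also have non-index lesions.
- ORR: RANO Evaluable set. Exposed through PR calls in those same subjects.

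**Step 4. How far the size depends on assumptions.** Assume 30% are truly progression-free after two scans, with equal risk at each scan. The per-scan risk is 1 - sqrt(0.30) = 0.452. Let s be the share without an index lesion and m the fraction of their progressions seen only as growth of existing non-index lesions. The estimate is s x (1 - (1 - m) x 0.452)^2 + (1 - s) x 0.30.

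| m | Squared term | s = 20% | s = 40% |
|---|---|---|---|
| 1/10 | 0.352 | 31% | 32% |
| 1/4 | 0.437 | 33% | 35% |
| 1/2 | 0.599 | 36% | 42% |

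All three inputs are assumptions; the documents give none of them.

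**Step 5. The one sized analysis that uses PR calls.** The Group 2 futility design reproduces. With stopping at 0/10, 1/19, 2/26 and 3/31, the exact binomial recursion gives type I error 0.0497 (stated 0.05), power 0.803 (stated 0.8), stopping at n=10 of 0.95^10 = 59.9% (stated 60%), and 15.55 - 6 = 9.55 additional subjects (stated 9.6). The gap changes none of these inputs. As an illustration only, if PR calls made despite progressing non-index disease raised the apparent ORR of an inactive treatment from 5% to 6%, 7%, 8% or 10%, the chance of acceptance would be 0.084, 0.128, 0.180 or 0.298. The documents give no rate for such calls.

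**The case against.** The strongest reply is that the reach is limited. The current protocol's landmark proportions exclude subjects without measurable disease. The wider population is in a SAP dated 20 May 2019, which cites the July 2017 protocol and predates Amendment 5. This stands and confines the main exposure to the SAP outputs. However, that is the only SAP supplied, and protocol section 10.5.1 itself defaults to the Safety Analysis Set, naming the RANO Evaluable set only for ORR.

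Second, T2/FLAIR worsening and clinical decline remain PD triggers, and the protocol synopsis dates PD from the first clinical or radiographic observation. T2/FLAIR will catch some cases. Clinical decline does not rescue the SAP endpoints as defined.

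Third, the 25% line speaks of enhancing disease rather than index lesions, so a reader might measure a remnant once it passes 10 mm. That is arguable, but the baseline definition gives no value to compare it with.

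Fourth, tolerance of new lesions may be deliberate, because the criteria are modified to capture pseudoprogression and delayed response. This stands against making the absence of new lesions a condition of PR. It does not explain ignoring progression of existing lesions, and PD already needs confirmation.

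Finally, these are secondary, descriptive endpoints in a phase 1 safety study, reported separately by arm. That limits the consequence.

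**Conclusion.** The gap is in the text of both documents. Unequivocal progression of a baseline non-index lesion is recorded but changes no PD or PR call. For subjects without index lesions it can push the SAP's Kaplan-Meier PFS and TTP upward. The direction is clear because a missing PD trigger can only delay or lose an event. The size is not known: Step 4 runs from 31% to 42% against an assumed true 30%, wholly on assumed inputs.

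A reader might infer three stronger things that the documents do not support:
- That subjects without index lesions have no imaging route to PD. They do, through T2/FLAIR worsening and progression in new lesions.
- That every progression-free estimate is inflated by these subjects. The protocol's 6- and 12-month proportions leave them out.
- That the inflation is 36% to 42%, or that ORR and the Group 2 type I error are shown to be wrong. The first is only the m = 1/2 row of Step 4; for the second, the stated design reproduces and no rate of affected PR calls is given.

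**What to change.** In protocol Table 22, SAP section 5 and SAP Appendix D:
1. Reword the third PD line as *or unequivocal progression of non-index lesions, whether present at baseline or new*, with the same confirmation at 4 weeks or later.
2. State that a subject meeting any confirmed PD line is not classed as PR at that assessment.
3. Do not make the absence of new lesions a condition of PR, but state whether the mere appearance of a new lesion is compatible with PR.
4. Reconcile Appendix D's requirement of at least one measurable lesion with criterion 107.
5. Reconcile the protocol and SAP populations for all progression-free estimates.

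The cost is wording in both documents, with no extra scan. A qualitative call adds some assessor variability, and reported PFS and TTP, possibly also ORR, may come out slightly lower. Response would have to be re-derived, from grades already recorded, for subjects already assessed. The protocol mentions 15 treated subjects and a first objective response, so this is modest work but not nil.
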